10.2.3 Efficacy Analysis Set (EAS)

The EAS will include all subjects randomized in Phase 2b or Phase 3 who:

- Received both doses of trial vaccine according to their randomization (2 doses of CVnCoV or 2 doses of placebo).
- Had not developed a virologically-confirmed case of COVID-19 before trial entry (based on Exclusion Criterion 1) or before 15 days following the second vaccination.
- Had not stopped the trial before 15 days following the second vaccination.
- Were SARS-CoV-2 naïve at baseline and Day 43 (based on seronegativity to N protein in the blood sample taken at baseline).

The EAS will be the primary analysis population for all efficacy endpoints (except for the key secondary efficacy endpoint related to seroconversion and for the efficacy endpoints evaluating efficacy starting after the first dose).

10.2.4 Per Protocol Efficacy Set (PPE)

The PPE set will include EAS subjects who meet all eligibility criteria at trial entry and who have no major protocol deviations that would impact the efficacy outcomes as specified in the SAP.

The PPE will be a supportive population for efficacy endpoints (except for the efficacy secondary endpoint evaluating efficacy starting after the first dose).

10.2.5 Per Protocol Immunogenicity Set (PPI)

The PPI set will include all Phase 2b subjects who belong to the Immunogenicity Subset (IS) (i.e. ~first 600 subjects enrolled into each of the 2 age groups in Phase 2b [18-60 and \geq 61 years of age]) and who:

- Received both doses as randomized and within the windows defined in the protocol.
- Have no major protocol deviations expecting to impact the immunogenicity outcomes as specified in the SAP.
- Have not received medical treatments (such as blood products, immunoglobulin therapy) that may interfere with one or both of the proposed immunogenicity measurements.
- Have at least 1 blood sample collected starting at 14 days (Day 43) post-second vaccination available for analysis.

The PPI will be the primary analysis population for SARS-CoV-2 RBD of S protein antibody responses and SARS-CoV-2 viral neutralizing antibody.

Subjects to be excluded from the PPE/PPI will be identified and reviewed at the Blinded Data Review Meeting held before unblinding of the trial. Major protocol deviations will be listed and summarized.

Clinical Trial Protocol	CV-NCOV-004
CureVac AG	COVID-19 mRNA Vaccine

Table 9 provides a summary of primary and supportive populations planned for analysis of each endpoint. Other analysis populations may be defined in the SAP.

Table 9Primary and Supportive Populations for the Analysis of Each
Endpoint

Endpoints	Primary Population	Supportive Population
Primary Efficacy Endpoint	EAS	PPE
Primary Safety Endpoints		
SAEs, AESI, medically-attended AEs	SAS	-
Solicited AEs	SASsol	-
Unsolicited AEs	SAS 2	-
AE leading to vaccine withdrawal	SAS	-
Secondary Efficacy Endpoints:		
Moderate to Severe COVID-19	EAS	PPE
Severe COVID-19	EAS	PPE
 eWild type" (i.e., WT/D614G lineages A.1/B.1 without VOC B.1.1.7 [Alpha], B.1.351 [Beta], B.1.429 [Epsilon]) and "UK" (B.1.1.7 [Alpha]) SARS-CoV-2 strains 	EAS	PPE
 COVID-19 in ≥ 61 years of age 	EAS (≥ 61 years of age subjects)	PPE (≥ 61 years of age subjects)
 All SARS-CoV-2 infection (RT-PCR positive) 	EAS	PPE
COVID-19 after first dose	SAS (naïve subjects)	-
Secondary Immunogenicity Endpoints:	•	
 SARS-CoV-2 RBD of spike (S) protein antibody responses 	PPI	-
SARS-CoV-2 viral neutralizing antibody	PPI	-
Exploratory Efficacy Endpoints:	1	
Severity of COVID-19	EAS	-
Any strain COVID-19	EAS	
 Supplemental oxygenation, hospitalization, mechanical ventilation, death 	EAS	SAS
COVID-19 after first dose	SAS	-

Endpoints	Primary Population	Supportive Population
 Second episode of COVID-19 	EAS	-
Exploratory Immunogenicity Endpoints:		
 RBD of S-specific T-cell response after antigen stimulation by intracellular cytokine staining (ICS) to investigate Th1 response and expression of Th2 	PPI	-
 The proportion of subjects with a detectable increase in SARS-CoV-2 RBD of S-specific T-cell response 	PPI	-

Additional populations that might be required for the analyses of the results from the open-label phase are of exploratory nature and will be defined in the SAP.

10.3 Statistical Analyses

10.3.1 General Considerations

Four analyses are planned: 2 interim analyses (when 56/111 cases are reached); the final analysis (when 160 cases are reached); and at the EOT. An SAP for the interim and final analyses will be prepared and finalized at the latest prior to database locks. This document will provide further details regarding the definition of analysis variables and analysis methodology to address all trial objectives and the handling of missing data.

For the open-label phase, analyses will be described by cohort. Details will be provided in an extended SAP.

10.3.2 Demographic, Medical History, and Other Baseline Characteristics

Data will be summarized with respect to demographic and baseline characteristics (e.g., age, gender, height, weight), medical history, baseline immune status, and all safety measurements using descriptive statistics (quantitative data) and contingency tables (qualitative data) overall, by vaccine group, and by age group and vaccine group.

10.3.3 Trial Vaccine Administration

The administrations of CVnCoV or control will be listed and the number of subjects actually receiving the vaccination doses will be summarized by vaccine group.

10.3.4 Concomitant Medication and Vaccinations

Concomitant medication/vaccination after the start of the trial will be listed and summarized by Anatomical Therapeutic Chemical term, overall and by vaccine group.

10.3.5 Efficacy Analyses

10.3.5.1 Primary Efficacy Endpoint Analysis

Primary Efficacy Analysis

In primary efficacy analysis, the VE, defined as the percent reduction in the frequency of any COVID-19 cases (according to primary case definitions) in vaccinated subjects

compared with subjects who received placebo will be calculated with exact 95%* CI as follows:

where

ARV = attack rate in vaccinated group = nv/Nv = number of subjects reporting at least 1 COVID-19 episode in the CVnCoV group / total follow-up time of evaluable subjects in the CVnCoV group (number of person-month).

ARP = attack rate in placebo group = np/Np = number of subjects reporting at least 1 COVID-19 episode in the placebo group / total follow-up time of evaluable subjects in the placebo group (number of person-month).

RR = relative risk = ARV/ARP

p = proportion of COVID-19 cases (according to primary case definition) coming from the CVnCoV group among all cases = nv/(nv+np).

r = ratio of total follow-up time of evaluable subjects in the CVnCoV group over total follow-up time of evaluable subjects in the placebo group = Nv/Np.

*Level of CI may be slightly adjusted due to the sequential design (see Section 10.3.8).

The statistical hypotheses for the primary efficacy endpoint is:

 H_{0A} : VE $\leq 30\%$ versus H_{1A} : VE > 30%

A is related to COVID-19 cases of any severity

The trial will be successful if either the lower limit of the exact 2-sided 95% (to be slightly adjusted to consider the sequential design) CI of VE endpoint is > 30% for all COVID-19 cases of any severity or if the lower limit of the exact 2-sided 95% CI of VE endpoint is > 20% for severe to moderate COVID-19 cases.

If the 2 interim analyses and the final analysis for COVID-19 cases of any severity are performed after 56/111 and 160 cases have been reported, respectively, the 1-sided α -risk to consider at the time of final analysis according to O'Brien-Fleming type error spending function will be 0.02281 and efficacy will be demonstrated at the final analysis if 53 cases or less over 160 are in the CVnCoV group (observed VE \geq 50.5%). To note, the rule in terms of split of cases to demonstrate efficacy can slightly differ if r \neq 1 (total follow-up time different in both groups).

Sensitivity Analysis

As a key sensitivity analysis, the time to first-occurrence of virologically-confirmed COVID-19 cases (according to primary case definitions) will be analyzed.

The Kaplan-Meier curves will display the estimated probabilities of not developing COVID-19 and log-rank test will be performed.

The time to first-occurrence of virologically-confirmed COVID-19 (date of symptoms onset) will start 15 days following the second vaccination.

Clinical Trial Protocol	CV-NCOV-004
CureVac AG	COVID-19 mRNA Vaccine

Subjects who do not develop COVID-19 will be censored at the date of trial termination or cut-off date for analysis whichever comes first.

An additional sensitivity analysis may include a Cox proportional hazards regression model adjusted for relevant baseline covariates specified in the SAP.

A subgroup analysis of region (LATAM vs EUROP) on the primary endpoint will also be performed.

More details on the analysis methods will be described in the SAP.

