The trial will be successful if the lower limit of the exact 2-sided 95% (to be slightly adjusted to consider the sequential design) CI of the VE endpoint of all COVID-19 cases of any severity is > 30% for H _{0A} or if the exact 2-sided 95% (to be slightly adjusted to consider the sequential design) CI of the VE endpoint of moderate to severe COVID-19 cases is > 20%. If the interim analyses and the final analysis are performed after 56/111 and 160 cases meeting the primary efficacy case definition have been reported, respectively, the 1-sided α -risk to consider at time of final analysis according to O'Brien-Fleming type error-spending-function will be 0.02281.
Efficacy will be demonstrated at the final analysis if 53 cases or less of the total 160 are in the CVnCoV group and if the follow-up time of evaluable subjects is equal in both groups (Nv=Np). At the first interim analysis, early high efficacy would be demonstrated if 9 cases or less of the 56 cases are in the CVnCoV group (observed efficacy \geq 80.9%); conversely, futility would be reached if 25 cases or more are in the CVnCoV group if Nv=Np.
At the second interim analysis, early high efficacy will be demonstrated if 32 cases or less of the 111 cases are in the CVnCoV group (observed efficacy \geq 59.5%); conversely, futility would be reached if 40 cases or more are in the CVnCoV group if Nv=Np.
For the key secondary endpoints, no interim analysis is planned. However, descriptive statistic as VE and 95% CI will be presented.
As a sensitivity analysis, the time to first-occurrence of virologically-confirmed COVID-19 cases (meeting the primary efficacy case definition) will also be analyzed. Kaplan-Meier curves will be displayed.
Statistical testing of the 3 key secondary efficacy endpoints will be performed according to the conditional hierarchical testing procedure using the order

[figure not shown]
Clinical Trial Protocol	CV-NCOV-004
CureVac AG	COVID-19 mRNA Vaccine

defined in the objectives and endpoints sections. Consequently:
• Efficacy of CVnCoV in regard to moderate and severe cases will be demonstrated only if there is successful demonstration of the primary efficacy objective.

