10 STATISTICAL CONSIDERATIONS

10.1 Sample Size Determination

10.1.1 Primary Efficacy Objective

This is an event-driven trial. Sample size and power considerations are based on the primary objective for demonstrating efficacy of CVnCoV in the prevention of virologically-confirmed cases of COVID-19 of any severity meeting the primary case definition. A group sequential design with 2 interim analyses for cases of COVID-19 of any severity demonstrating a high level of efficacy or reaching futility is planned using O'Brien and Fleming type error-spending-function [36] and the sample size is based on the test for one single proportion (i.e. the proportion of cases in the CVnCoV group, among all cases). The group sequential design is based on the any severity COVID-19 endpoint, due to the higher case number required to meet this endpoint.

With an overall 2-sided alpha of 5%, a total of 160 COVID-19 cases of any severity (meeting the primary efficacy case definition for COVID-19 of any severity) are needed at final analysis, to have a power of 90% to demonstrate the VE is above 30% based on the lower bound of the CI for VE, when considering the VE under the alternative hypothesis is 60% (i.e. equivalently to demonstrate the proportion of cases in the CVnCoV group is below 0.4118, based on the upper bound of the CI for proportion when considering the proportion under the alternative hypothesis is equal to 0.2857).

The 2 interim analyses for high efficacy or futility of the primary objective of COVID-19 cases of any severity will be performed once 56/111 cases have been accrued and adjudicated (approximately 30/60% of cases).

Assuming an incidence rate of COVID-19 of 0.15% per month in placebo subjects, an overall non-evaluable rate of 20% (corresponding to subjects excluded from the EAS and drop-outs) and a VE of 60%, 36,500 subjects enrolled over approximately 3 months (18,250 per vaccine group) will accrue 160 COVID-19 cases of any severity at approximately 9 months after the first vaccination. A lower incidence rate, a longer enrollment duration, or a higher non-evaluable rate or VE will delay the acquisition of the 160 cases and the time of final analysis. Subjects will be randomized to receive either CVnCoV or placebo in a 1:1 ratio, stratified by country and age group (18 to 60 and \geq 61 years of age).

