10.3.5.2 Secondary Efficacy Endpoints Analyses

Statistical testing of the 3 key secondary efficacy endpoints will be performed according to the conditional hierarchical testing procedure using the order defined in the objective/endpoints sections. Consequently:

- Efficacy of CVnCoV in regard to moderate and severe cases will be demonstrated only if there is successful demonstration of the primary efficacy objective.
- Efficacy of CVnCoV in regard to severe cases will be demonstrated only if there is successful demonstration of the primary efficacy objective and the key secondary objective on moderate and severe cases.
- Efficacy of CVnCoV in regard to (RT-PCR positive) cases of "wild type" (i.e., WT/D614G lineages A.1/B.1 without VOC B.1.1.7 [Alpha], B.1.351 [Beta], B.1.429 [Epsilon]) and "UK" (B.1.1.7 [Alpha]) will be demonstrated only if there is successful demonstration of the primary efficacy objective and the key secondary objective on moderate and severe cases and severe cases.

Otherwise, these endpoints will be analyzed as exploratory endpoints without success criteria testing.

To assess the efficacy in the prevention of "wild type" (i.e., WT/D614G lineages A.1/B.1 without VOC B.1.1.7 [Alpha], B.1.351 [Beta], B.1.429 [Epsilon]) and "UK" (B.1.1.7 [Alpha]) cases, moderate to severe, severe disease and asymptomatic infections, similar analyses to those performed on the primary efficacy endpoint will be performed. The efficacy will be demonstrated if the lower limit of the exact 2-sided 95% CI of VE is above 30% for "wild type" (i.e., WT/D614G lineages A.1/B.1 without VOC B.1.1.7 [Alpha], B.1.351 [Beta], B.1.429 [Epsilon]) and "UK" (B.1.1.7 [Alpha]) cases, 20% for moderate to severe disease, 10% for severe disease and above 0% for asymptomatic infections.

Other secondary efficacy endpoints will be analyzed similarly to the primary efficacy endpoint but no formal testing will be performed for those endpoints. For efficacy after the first dose, the time to first-occurrence of virologically-confirmed COVID-19 (date of symptom onset) will start after the first vaccination. The BoD will be analyzed using 2 different scoring systems. Both BoD scoring systems place more weight on efficacy against severe COVID-19 or severe disease as reflected by hospitalization or death. In addition, VE and associated CI will be calculated for each of the BoD categories.

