*Rules in terms of split of cases to demonstrate efficacy/futility can slightly differ if the total number of evaluable subjects is unequal in both groups ($r \neq 1$).

If the interim analysis is performed exactly after 56/111 cases have been reported, a 1-sided p-value lower than 0.00015/0.00707 (i.e. lower limit of the 2-sided 99.99/99.3% Cl > 30%) will lead to the conclusion of high efficacy, while a 1-sided p-value higher than 0.66345/0.12356 will result in the demonstration of futility. Otherwise, the final analysis will be performed at 160 cases. Similarly, if the number of evaluable subjects is equal in both groups, it means that the trial will conclude early high efficacy if 9/32 cases or less over 56/111 are coming from the CVnCoV group, while futility of the trial will be demonstrated if 25/40 cases or more are coming from the CVnCoV group.

Of note, the actual boundaries used for decision making would depend on the exact number of cases occurring and reported at each analysis (interim and final).

The boundaries will be applied in a nonbinding way as there are many other factors that would be part of the decision-making process.

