12.6.2 Primary Efficacy Endpoint Analysis

12.6.2.1 Primary Efficacy Analysis

The primary endpoint in this trial is the occurrence of first episodes of virologically-confirmed cases of COVID-19 of any severity meeting the case definition for the primary efficacy analysis (see Section 10.7.4).

From the number of occurrences of COVID-19 cases in each vaccine group, the VE corresponding to the endpoint is calculated as follows:

$$VE = 1 - \frac{p}{1-p} * \frac{1}{r}$$

Thereby, p denotes the proportion of cases coming from the CVnCoV group among all cases and r is the ratio of total follow-up time of subjects in the CVnCoV group over the total follow-up time of subjects in the placebo group (see Section 10.13).

The statistical hypothesis for the primary efficacy endpoints is:

$$H_{0A}: VE \leq 30\% \text{ vs. } H_{1A}: VE > 30\%$$

Or, equivalently:

$$H_{0A}: p \geq \frac{0.7}{\frac{1}{r} + 0.7} \text{ vs. } H_{1A}: p < \frac{0.7}{\frac{1}{r} + 0.7}$$

Thereby, A refers to the endpoint of COVID-19 cases of any severity.

It should be noted that the above reduces to

$$H_{0A}: p \geq 0.4118 \text{ vs. } H_{1A}: p < 0.4118,$$

if the total follow-up time is the same in both groups, i.e. if r equals 1.

For the primary analysis, the above hypotheses are tested via an exact test for Binomial proportions on p. with an overall 2-sided significance level of 5% (or equivalently, a 1-sided 2.5% level of significance).

Given the IA stopping rules for the primary endpoint of COVID-19 cases of any severity, if the final primary efficacy analysis is performed at 160 cases, the tests are performed with a 1-sided 2.281% level of significance, to keep the type I error rate for this endpoint at 5% (2-sided). See also Section 11.0 for further details.

An exact two-sided 95.438% Pearson-Clopper CI for p is calculated. From this, the LL and Upper Limit (UL) of the 95.438% CI for the VE is calculated from the UL and LL of the CI for p as:

$$LL_{VE} = 1 - \frac{UL_p}{(1 - UL_p) * r}; \quad UL_{VE} = 1 - \frac{LL_p}{(1 - LL_p) * r}$$

Efficacy on this primary endpoint is demonstrated at the final primary efficacy analysis if the UL of the 95.438% CI for p is below 0.4118. Note that this is equivalent to the LL of the 95.438% CI for the VE being above 30%.

The trial is successful if efficacy is demonstrated on the primary endpoint.

The following is presented for the analysis of the primary endpoint:

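### The protocol counts the trial a success on either the primary endpoint or moderate-to-severe cases, each at full alpha, against its own testing hierarchy and the SAP

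*Protocol*

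**What the plan says.** Four places define success or decide when moderate-to-severe disease may be claimed.

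- **Protocol 10.3.5.1.** The rule opens with "The trial will be successful if either the lower limit of the exact 2-sided 95% (to be slightly adjusted to consider the sequential design"), sets 30% as the bar for any severity, and goes on: "or if the lower limit of the exact 2-sided 95% CI of VE endpoint is > 20% for severe to moderate COVID-19 cases".
- **Protocol synopsis, efficacy analyses.** The same alternative appears, with the second branch worded as "CI of the VE endpoint of moderate to severe COVID-19 cases is > 20"%. Here the note about a slight adjustment for the sequential design is attached to the second interval as well, but no adjusted level is given.
- **Protocol 10.3.5.2.** "Efficacy of CVnCoV in regard to moderate and severe cases will be demonstrated only if there is successful demonstration of the primary efficacy objective". If the primary fails, the key secondary endpoints become exploratory and carry no success criterion. The synopsis contains the same hierarchy, a few lines below the either/or rule.
- **SAP 12.6.2.1.** "The trial is successful if efficacy is demonstrated on the primary endpoint". SAP 12.6.1 and 12.6.3.1 test the key secondary endpoints at 5% two-sided, and only after primary success.

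The whole type I error goes to the primary endpoint. Protocol 10.1.1 states "With an overall 2-sided alpha of 5%, a total of 160 COVID-19 cases of any severity", and section 10.3.8 spends that alpha over looks at 56, 111 and 160 cases. SAP 6.2, which lists intended departures from Protocol 4.0, does not mention a different success rule.

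**The concern.** A rule that accepts either of two tests needs an alpha split or some other multiplicity adjustment. Here the primary uses the full one-sided 2.5%, and section 10.3.5.1 gives the second route another 2.5%. The chance of declaring success when neither null is false therefore exceeds the stated level.

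The contradiction also has a direct consequence. If any-severity disease misses its bar and moderate-to-severe disease clears 20%, section 10.3.5.1 and the synopsis call the trial successful, while section 10.3.5.2 and the SAP allow no claim at all. A pivotal protocol should not leave its success criterion open to two opposite readings.

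**Working it through.** **Inputs**

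| Item | Value | Source |
|---|---|---|
| Primary null | VE 30%, case share 0.4118 | Protocol 10.1.1 |
| Final look | one-sided 0.02281, success at 53 or fewer of 160 | Protocol 10.3.5.1 |
| Interim looks | one-sided 0.00015 (9 or fewer of 56) and 0.00707 (32 or fewer of 111) | Protocol 10.3.8 |
| Moderate-to-severe cases | 53 of the 160 | Protocol 10.1.2 |
| Moderate-to-severe test | lower 95% limit above 20%; power 91.5% at VE 70% | Protocol 10.1.2 |

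With equal follow-up in the two groups (r = 1), the CVnCoV share of cases is p = (1 − VE)/(2 − VE):

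- VE 30%: 0.7/1.7 = 0.4118
- VE 20%: 0.8/1.8 = 0.4444
- VE 70%: 0.3/1.3 = 0.2308

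**Step 1. Reproduce the plan's own figures.** O'Brien-Fleming-type spending at 56/160, 111/160 and 160/160 gives 0.00015, 0.00707 and 0.02281, as stated. The exact binomial cut-offs are 9, 32 and 53, as stated. For moderate-to-severe disease:

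- P(X ≤ 16 | 53, 0.4444) = 0.0242 and P(X ≤ 17) = 0.0457, so the cut-off is 16 of 53.
- Power at VE 70% is P(X ≤ 16 | 53, 0.2308) = 0.9147, against the stated 91.5%.

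**Step 2. Either/or rule at the final look, both nulls at their margins.** The 53 cases are nested in the 160. For the overall share to be 0.4118, the share among the other 107 cases must be (160 × 0.4118 − 53 × 0.4444)/107 = 0.3956. Then, exactly:

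- P(primary succeeds: 53 or fewer of 160) = 0.0223
- P(moderate-to-severe succeeds: 16 or fewer of 53) = 0.0242
- P(both) = 0.0054
- P(either) = 0.0223 + 0.0242 − 0.0054 = **0.0411**, against 0.025 intended

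**Step 3. Vary the setting, both nulls still at their margins.**

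| Setting | P(declare success), one-sided |
|---|---|
| Either/or, three looks, 53 of 160 fixed (simulation) | 0.0420 |
| Either/or, three looks, random number of moderate-to-severe cases, averaging 1/5, 1/3 or 1/2 of the total (simulation) | 0.037, 0.037, 0.036 |
| Either/or, nominal 0.025 for each, bivariate normal, correlation √(53/160) = 0.576 | 0.0442 |
| Primary only, three looks (exact) | 0.0236 |
| Primary only, three looks, futility stops followed (exact) | 0.0214 |

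**Step 4. How often would the two rules disagree?** Take any-severity VE at exactly 30%, so the primary null is true, with 53 of 160 cases moderate-to-severe:

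- Moderate-to-severe VE 50%: the either/or rule declares success with probability 0.375 (exact, final look).
- Moderate-to-severe VE 70%, the protocol's planning value: 0.915.

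These two are not type I errors for moderate-to-severe disease, because that null is false in both. They show how often the protocol's rule could call the trial successful when the hierarchy and the SAP should almost never do so.

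**The case against.** The strongest reply is that the clause no longer decides anything. Protocol 4.0 was issued after the final efficacy analysis. Its section 3.1.4 reports VE of 48% with a 95.826% interval of 31.0% to 61.4%, so the primary endpoint cleared 30% by itself. The open-label phase has no inferential efficacy analysis. The SAP, whose versions 3.0 and 4.0 were approved before unblinding for the final primary analysis, uses the primary-only rule. The amendment history says moderate-to-severe disease was moved from co-primary to secondary in order to preserve alpha, so the clause looks like a leftover. All of this is fair and limits the practical effect.

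A second reply is that 4% is a worst case. Any-severity VE of 30% with moderate-to-severe VE of 20% implies VE of 34.6% against mild disease, from 1 − 0.3956/0.6044. That is better protection against mild than against more serious illness. If VE is 20% throughout, the exact final-look figure is 2.55%, or 2.6% with interim looks. This is also true, but a claim of type I error control has to hold under the least favourable null.

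Third, the synopsis says the second interval is to be slightly adjusted too. It gives no level, and the adjustment it names is for interim looks rather than for a second route to success, so it does not repair the rule.

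None of these points removes the contradiction. The lower limit cleared its margin by only 1.0 percentage point, and SAP 12.6.1 leaves open re-running some primary outputs after the unblinding dates for site AR009 were corrected.

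**Conclusion.** The concern holds. The either/or success rule is in the current protocol text, conflicts with the protocol's own hierarchy, and conflicts with the SAP without being listed as an intended departure. Taken literally, it raises the one-sided probability of false success from 2.4% to about 4% (4.1% to 4.2% for the planned split, 3.6% to 3.7% with a random split). These figures assume equal follow-up in the two groups and both true efficacies exactly at their margins. The reported primary result did not depend on the clause, and alpha is controlled under the rule in the SAP. What is wrong is the decision rule in the protocol.

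**What to change.** Delete the moderate-to-severe alternative from the success sentence in Protocol 10.3.5.1 and from the matching sentence in the synopsis. In both places, state that the trial succeeds if the lower limit of the sequentially adjusted exact interval for VE against COVID-19 of any severity exceeds 30%, and that moderate-to-severe disease (bar 20%) is tested only after that, as section 10.3.5.2 sets out. This brings the protocol into line with SAP 12.6.2.1 and needs no change to data, sample size or analyses. The sponsor gives up a second route to declaring success.

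If two routes were really intended, alpha would have to be split between them, and section 10.3.5.2, the boundaries, the power statements and the SAP rewritten to match.
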